6.12.3. Deaths

The listing of all deaths by patient for all enrolled patients will be provided as part of the SAE listing, regardless of the investigator's or the sponsor's judgment about causality. Each listing will include study ID, investigator ID, patient ID, treatment group, baseline age, sex, associated AE, first and last dose date for open label insulin lispro and randomized IP, and the event date.

6.12.4. Hypoglycemic Events and Other Adverse Events

The analysis plans for the following adverse events are discussed in Section 6.12.4.1 through Section 6.12.4.4:

- hypoglycemic events
- systemic hypersensitivity reaction
- injection site reaction

- hepatobiliary events

These AE analyses will be similar to the TEAE analyses. Refer to [Table 6.5](#) for the requirement of analysis data for a specific analysis period.

6.12.4.1. Hypoglycemic Events

Hypoglycemia events that occur during the study outside the MMTT will be captured using an eCOA diary starting from Visit 2 through Visit 801. Whenever hypoglycemia is suspected, the patient should record the blood glucose value, any associated symptoms, and the treatment administered in eCOA. A set of events is counted as 1 event in analysis if it consists of an originating event and subsequent continuing events as marked by the patient in eCOA, or the duration between adjacent events is ≤ 30 minutes. The event with the highest severity will be selected for analysis with severity determined in the order of: 1) it is a severe hypoglycemia, 2) it has symptoms of hypoglycemia reported, and 3) it has the lowest blood glucose value. If there are multiple events tied in all 3 aspects, the event with the largest number of non-missing responses to the questions of nocturnal hypoglycemia and postmeal time frame will be selected. If there are still multiple events tied, the latest event (based on data entry time) will be selected.

The following types of hypoglycemia events will be derived in the analysis data sets: documented hypoglycemia, severe hypoglycemia, nocturnal hypoglycemia (documented and occurring between bedtime and waking), probable symptomatic hypoglycemia, and overall hypoglycemia. Only severe hypoglycemia will be collected as AEs and all episodes of severe hypoglycemia will be considered as SAEs. Documented hypoglycemia (including documented symptomatic hypoglycemia, documented asymptomatic hypoglycemia and documented unspecified hypoglycemia) will be based on blood glucose (BG) ≤ 70 mg/dL. In addition, documented clinically significant hypoglycemia with similar criterion as above documented hypoglycemia except for the threshold of BG < 54 mg/dL will be summarized. Hypoglycemia identified by CGM for patients in the CGM Addendum will not be included in these analyses.

[Table 6.6](#) provides detailed statistical methods for each endpoint related to hypoglycemia. For these analyses, hypoglycemia events prior to discontinuation of IP will be summarized. For the analysis period prior to Week 26, the analysis data will include data from all 3 treatment groups. For the analysis period after Week 26, the analysis data will only include data from the 2 double-blind treatment groups. Additional analyses for other types of hypoglycemic events not mentioned in the table and for the post-treatment period may be conducted as needed.

The incidence and number of episodes of hypoglycemia (regardless of the type of hypoglycemia event) during the MMTT will be summarized by treatment and time relative to the meal (≤ 0.5 , ≤ 1 , ≤ 2 , ≤ 4 , >1 to ≤ 2 and >2 to ≤ 4 hours after start of the meal) and analyzed by Fisher's exact test.

A listing of patients with at least 1 severe hypoglycemia reported (as SAE) after randomization will be provided.

A list of MedDRA PTs will be used for the narrow search of potential severe hypoglycemia in spontaneously reported AEs. The events identified through the search strategy that are also

reported as SAEs will be summarized and compared between treatments. Fisher's exact test will be used to assess the treatment difference in the proportion of patients with potential severe hypoglycemia.

Table 6.6. Summary of Analyses for Endpoints Related to Hypoglycemia

Endpoint	Analysis Period	Statistical Method
Rate of hypoglycemic events (per patient per 30 days / year) All Documented ^a Nocturnal ^a Documented Symptomatic ^a Overall Non-Nocturnal (or Daytime) (Documented and between waking and bedtime) ^a Probable Symptomatic	0-4, 0-12, 0-26, 4-8, 8-12, 12-26, 26-52, 0-52 weeks	Negative binomial regression with treatment, and baseline hypoglycemia event rate with the same category of the dependent variable as covariates, log (exposure/30/365.25 days) as the offset in the model.
Incidence of hypoglycemic events All Documented ^a Nocturnal ^a Documented Symptomatic ^a Overall Non-Nocturnal (or Daytime) (Documented and between waking and bedtime) ^a Probable Symptomatic	0-4, 0-12, 0-26, 4-8, 8-12, 12-26, 26-52, 0-52 weeks	Logistic regression with treatment, baseline hypoglycemia event rate with the same category of the dependent variable as covariates.
Rate of postmeal hypoglycemic events (per patient per 30 days / year) for all 3 main meals Documented Symptomatic ^a Documented Asymptomatic ^a	≤ 0.5 , ≤ 1 , ≤ 2 , ≤ 4 , >1 to ≤ 2 and >2 to ≤ 4 hours after start of a meal within 0-12, 12-26, 0-26, 26-52, 0-52 weeks	Negative binomial regression with treatment, baseline postmeal hypoglycemia event rate with the same category of the dependent variable as covariates, log (exposure/30/365.25 days) as the offset in the model.
Incidence of postmeal hypoglycemic events for all 3 main meals Documented Symptomatic ^a Documented Asymptomatic ^a	≤ 0.5 , ≤ 1 , ≤ 2 , ≤ 4 , >1 to ≤ 2 and >2 to ≤ 4 hours after start of a meal within 0-12, 12-26, 0-26, 26-52, 0-52 weeks	Logistic regression with treatment, baseline postmeal hypoglycemia event rate with the same category of the dependent variable as covariates.
Rate of severe hypoglycemic events (per patient per year / 100 years)	0-12, 0-26, 12-26, 26-52, 0-52 weeks	Exposure adjusted rate per year / 100 years (calculated by total number of events divided by total exposure for individual patients) will be provided and the empirical method (see Appendix 1 for details) will be used for treatment comparison.

Summary of Analyses for Endpoints Related to Hypoglycemia

Endpoint	Analysis Period	Statistical Method
Incidence of severe hypoglycemic events	0-12, 0-26, 12-26, 26-52, 0-52 weeks	Proportion of patients with severe hypoglycemia will be reported. The treatment comparison will be based on a logistic regression model with treatment and baseline rate as a covariate.
Rate of postmeal severe hypoglycemic events (per patient per year / 100 years) for all 3 main meals	0-12, 12-26, 0-26, 26-52, 0-52 weeks	Due to limit data for the rare event, only summary statistics will be provided by treatment. No statistical comparison will be conducted.
Incidence of postmeal severe hypoglycemic events for all 3 main meals	0-12, 12-26, 0-26, 26-52, 0-52 weeks	Fisher exact test will be used for treatment comparison.

^a All documented hypoglycemia and the subcategories based on the thresholds of blood glucose ≤ 70 mg/dL and blood glucose < 54 mg/dL will be analyzed, except for postmeal hypoglycemia for which only the threshold of ≤ 70 mg/dL will be applied.

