5. (H5) To test the hypothesis that LY900014 administered as postprandial insulin 20 minutes after the start of a meal, (LY900014+20), is noninferior to insulin lispro, administered as prandial insulin, on glycemic control (NIM=0.4% for HbA1c)	5. Difference between LY900014+20 and insulin lispro in change from baseline to Week 26 in HbA1c
Other Secondary Objectives	
6. To compare LY900014+20 with insulin lispro and LY900014 with respect to 1-hour and 2-hour PPG excursions	6. 1- and 2-hour PPG excursions from an MMTT test at Week 26
7. To compare the glycemic control of LY900014 with LY900014+20	7. Change from baseline HbA1c values at Week 26
8. To compare LY900014, LY900014+20, and insulin lispro on the rate of severe hypoglycemic events	8. Rate (events/patient/100 years) of severe hypoglycemic events from baseline through Week 26 and Week 52

Objectives and Endpoints

Objectives	Endpoints
Other Secondary Objectives (continued)	
9. To compare LY900014, LY900014+20, and insulin lispro with respect to the incidence and rate of documented symptomatic postmeal hypoglycemia	9. Rate (events/patient/year and/or events/patient/30 days) and incidence (percent of patients with at least 1 event) of documented symptomatic postmeal hypoglycemia within 1 and 2 hours after start of a meal from Week 12 through Week 26, Week 0 through Week 26, Week 26 through Week 52, and Week 0 through Week 52
10. To compare LY900014, LY900014+20, and insulin lispro with respect to the incidence and rate of documented symptomatic hypoglycemia	10. Rate (events/patient/year and/or events/patient/30 days) and incidence (percent of patients with events) of documented symptomatic hypoglycemic events from Week 12 through Week 26, Week 0 through Week 26, Week 26 through Week 52, and Week 0 through Week 52
11. To compare LY900014, LY900014+20, and insulin lispro with respect to 1,5-AG	11. Change from baseline 1,5-AG values at Week 26 and Week 52
12. To compare LY900014, LY900014+20, and insulin lispro with respect to 10-point SMBG profiles	12. Change from baseline 10-point SMBG values at Week 26 and Week 52
13. To compare LY900014, LY900014+20, and insulin lispro with respect to total, basal, and prandial insulin dose	13. Change from baseline in total, basal and prandial insulin doses and prandial/total insulin dose ratios at Week 26 and Week 52

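### Representing merged hypoglycemia entries by one selected entry can drop episodes from the <54 mg/dL, all-documented and overall counts

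*SAP*

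**What the plan says.** **Counting.** SAP 6.12.4.1 states: "A set of events is counted as 1 event in analysis if it consists of an originating event and subsequent continuing events". Adjacent entries 30 minutes or less apart are also merged.

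**Selection.** "The event with the highest severity will be selected for analysis with severity determined in the order of": severe first, then "2) it has symptoms of hypoglycemia reported, and 3) it has the lowest blood glucose value". For ties on all three, "the event with the largest number of non-missing responses to the questions of nocturnal hypoglycemia and postmeal time frame will be selected", and after that the latest by data entry time.

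**Categories.** The SAP then derives documented (≤70 mg/dL), severe, nocturnal, probable symptomatic and overall events. It adds "documented clinically significant hypoglycemia with similar criterion as above documented hypoglycemia except for the threshold of BG" <54 mg/dL. Table 6.6 footnote a applies both thresholds to the documented categories, "except for postmeal hypoglycemia for which only the threshold of" ≤70 mg/dL is used.

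**Definitions.** Protocol 9.4.1 calls symptoms without a glucose value probable symptomatic. It calls symptoms with a value above 70 mg/dL relative hypoglycemia, which is left out of overall hypoglycemia. It notes that a severe event may have no glucose value.

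The SAP does not say how a missing glucose ranks under the third criterion, or whether a merged event takes its time from its onset or from the selected entry.

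**The concern.** A merged set is one clinical episode, but the rule reduces it to one diary entry. Symptoms rank above glucose, so a symptomatic entry with a mild, missing or >70 mg/dL value displaces a lower asymptomatic value in the same episode. A severe entry displaces everything else. The deeper reading then plays no part in classification.

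The <54 mg/dL, all-documented and overall categories are reported as rates and incidences for all three arms. The lead-in rate in the same category is the model covariate (SAP 6.2, Table 6.6), so it carries the same misclassification.

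**Working it through.** The plan states no figure for this rule, so there is none to reproduce. The check applies the selection order to example sets and classifies the selected entry by Protocol 9.4.1 and SAP 6.12.4.1. Missing glucose is ranked last, which is an assumption.

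| Set | Entries (mg/dL, minutes after meal) | Selected | Result |
|---|---|---|---|
| A | no symptoms 50 at 45; symptoms 65 at 65 | 65 | <54 status lost |
| B | no symptoms 62 at 45; symptoms, no glucose at 65 | no glucose | documented lost; becomes probable symptomatic, still in overall |
| C | no symptoms 66 at 45; symptoms 74 at 65 | 74 | documented and overall lost; becomes relative |
| D | symptoms 50 at 45; severe, no glucose at 65 | severe | documented symptomatic and <54 lost; still severe and overall |
| E | symptoms 64 at 50; symptoms 58 at 75 | 58 | no glucose category lost; ≤1 hour or >1 to ≤2 hours, depending on which time is used |
| F | symptoms 50 at 45; no symptoms 48 at 65 | 50 | nothing lost |
| G | symptoms 50 at 45; symptoms 62 at 65 | 50 | nothing lost |

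The loss is therefore conditional. A severe or symptomatic entry with a higher, missing or >70 value must outrank the entry that qualifies.

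**Illustrative size, model 1.** Two-entry sets. The first entry is symptomatic with glucose uniform on 45–70. The recheck comes 15 minutes later with a normal change of mean 0 and SD 8. Symptoms are ticked at 50% or 80% of rechecks. A <54 episode is lost when the first value is ≥54, the recheck is <54 and the recheck is asymptomatic.

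- P(first <54) = 9/25 = 0.360.
- P(first ≥54, recheck <54) = (8/25) × ∫₀² Φ(−u) du = 0.32 × 0.3905 = 0.125.
- P(any <54) = 0.360 + 0.125 = 0.485.
- Loss = (1 − p) × 0.125/0.485 = (1 − p) × 0.258. This is 12.9% at p = 0.5 and about 5% at p = 0.8.

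The zero mean change matters, because patients are told to treat values ≤70. Simulating with an assumed mean rise gives a loss of 2.5–6.2% at +5 mg/dL, about 1–2% at +10 and 0.2–0.5% at +15.

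**Illustrative size, model 2.** Two non-severe entries, each with glucose of mean 60 and SD 8 (asymptomatic values capped at 70). Symptoms are present in 30–70% of entries, and 0–20% of symptomatic entries have no glucose.

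- Of sets with a <54 entry, 18–25% lose that status.
- Of sets with a documented entry, 4–15% lose it.
- Of sets in which one entry has both symptoms and a value ≤70, 0% lose documented symptomatic status.

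**Timing.** With onset uniform over 0–2 hours after the meal, if the selected entry's time is used:

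- Model 1 moves 6–10% of episodes starting within 1 hour out of that window at zero mean change, and 0.4–0.6% at +15 mg/dL.
- Model 2, with entries 5–30 minutes apart, gives a window different from onset in about 14% of sets.

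All percentages apply to two-entry sets only.

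**The case against.** The strongest defense is that ranking symptoms second protects endpoint 10. When one entry has both symptoms and a value ≤70, a symptomatic entry is always selected ahead of an asymptomatic one, and the lowest glucose among symptomatic entries is kept. Model 2 confirms this with 0% loss. It stands, with two limits: a severe entry without a qualifying glucose (set D), and the unstated ranking of missing glucose. If missing sorted as lowest, a symptomatic entry without a value would beat a symptomatic 58.

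Other points also stand. Set D still counts as severe, as an SAE and in overall hypoglycemia. The <54 threshold is not applied to postmeal events, so that loss cannot touch "documented symptomatic postmeal hypoglycemia within 1 and 2 hours after start of a meal" (endpoint 9). The hypoglycemia endpoints carry no multiplicity adjustment (SAP 6.5), and the same rule applies in every arm.

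A reader might infer three stronger points that the documents do not support:

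- **Set B is a lost documented symptomatic event.** That needs symptoms from one entry combined with glucose from another. Protocol 9.4.1 requires the symptoms to be accompanied by the low value, and neither document says to judge this across entries.
- **Postmeal events go to the wrong window.** The SAP never defines the time of a merged event. The tie-break shows that the postmeal and nocturnal answers sit on each entry, so a shift is plausible, but the fault is an unspecified rule.
- **Early postmeal risk with LY900014 is understated.** The documents give no onset distribution by arm, and a loss in equal proportion would leave a rate ratio unchanged.

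None of this restores the categories lost in sets A to D.

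**Conclusion.** The point holds in limited form. Read literally, SAP 6.12.4.1 gives wrong counts for some merged episodes in the <54, all-documented and, through relative hypoglycemia, overall categories. The documented symptomatic ≤70 endpoint is mostly safe, provided missing glucose ranks last. The time that sets the postmeal and nocturnal classification of a merged event is undefined.

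The size is unknown. For <54 status the illustrative loss runs from 0.2% to 25% of two-entry episodes reaching that level. It depends on the assumed glucose change, symptom reporting and missing values. The overall effect scales with the share of multi-entry episodes, which the documents do not give. Neither the existence nor the direction of a between-arm effect can be derived.

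**What to change.** Keep the continuing-entry and 30-minute rules for counting 1 event. Replace single-entry selection with episode-level classification:

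- Severe if any entry is severe.
- Documented (≤70) and <54 if any entry's glucose meets the threshold.
- Documented symptomatic if any single entry has both symptoms and a qualifying glucose, as in Protocol 9.4.1.
- Overall if any entry qualifies.
- Where values must be ranked, missing glucose ranks last.
- Postmeal and nocturnal classification from the originating entry, or the first non-missing answer if that is blank.

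Apply the same derivation to the lead-in baseline rate.

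Under this rule set A keeps <54, set B keeps documented, set C keeps documented and overall, and set D keeps documented symptomatic and <54 as well as severe. Set E takes the ≤1 hour window if the originating entry carries that answer.

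The cost is SAP wording and a small change to the derivation program, with no new data. Counts in some categories rise slightly.

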9.4. Safety

9.4.1. Hypoglycemia

Patients are encouraged to perform SMBG, whenever hypoglycemia may be suspected, either by symptoms experienced or perceived increased risk as related to dietary intake, physical activity, or inadvertent or atypical insulin dosing. All patients will be instructed to treat a BG ≤ 70 mg/dL (3.9 mmol/L) as hypoglycemia.

Hypoglycemia events will be collected in eCOA (see Section 9.1.4.1). If a hypoglycemia event is suspected, the patient should record the BG value, any associated symptoms, and the treatment administered in eCOA. The patient should contact the site as necessary. Reports of hypoglycemia will be classified by the investigator as “severe” or “not severe” based upon data collected in eCOA and in consultation with the patient; see below and Section 9.2.1. All episodes of severe hypoglycemia must be reported as AEs via electronic data entry and as SAEs.

Hypoglycemia will be described using the following definitions:

- **Documented hypoglycemia:**
 - **Documented symptomatic hypoglycemia:** an event during which typical symptoms of hypoglycemia are accompanied by BG ≤ 70 mg/dL (3.9 mmol/L).
 - **Documented asymptomatic hypoglycemia:** an event not accompanied by typical symptoms of hypoglycemia but with BG ≤ 70 mg/dL (3.9 mmol/L).
 - **Documented unspecified hypoglycemia:** an event during which BG ≤ 70 mg/dL (3.9 mmol/L) but no information relative to symptoms of hypoglycemia were recorded.
- **Probable symptomatic hypoglycemia:** an event during which symptoms are indicative of hypoglycemia and which was presumably caused by BG ≤ 70 mg/dL (3.9 mmol/L), although no BG measurement was reported.
- **Severe hypoglycemia:** an event requiring assistance of another person to actively administer carbohydrate, glucagon, or other resuscitative actions. During these episodes, the patient has an altered mental status and cannot assist in his/her own care, may be semiconscious or unconscious, or experience coma with or without seizures, and may require parenteral therapy. BG measurements may not be available during such an event, but neurological recovery attributable to the restoration of BG concentration to normal is considered sufficient evidence that the event was induced by a low BG concentration (BG ≤ 70 mg/dL [3.9 mmol/L]).
- **Nocturnal hypoglycemia:** any hypoglycemic event (documented hypoglycemia or probable symptomatic hypoglycemia, including severe hypoglycemia) that occurs between bedtime and waking.

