- **Relative hypoglycemia:** an event during which typical symptoms of hypoglycemia, that do not require the assistance of another person, are accompanied by BG > 70 mg/dL (3.9 mmol/L), but these levels may be quickly approaching the 70 mg/dL (3.9 mmol/L) threshold.
- **Overall hypoglycemia:** This category combines all cases of hypoglycemia (documented hypoglycemia and probable symptomatic hypoglycemia, including

severe hypoglycemia) excluding the events of relative hypoglycemia. If an event of hypoglycemia falls into multiple subcategories, the event is only counted once in this category.

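### The SAP counts nocturnal hypoglycemia only when a low glucose value was recorded, which is narrower than Protocol 9.4.1, and gives no justification

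*SAP*

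**What the plan says.** Protocol 9.4.1 defines nocturnal hypoglycemia as "any hypoglycemic event (documented hypoglycemia or probable symptomatic hypoglycemia, including severe hypoglycemia) that occurs between bedtime and waking". A glucose value is not required. The same section describes two kinds of event that can lack one. Of severe events it says that "BG measurements may not be available during such an event", and it accepts neurological recovery as sufficient evidence of a low glucose. Probable symptomatic events are those presumed to be caused by low glucose, "although no BG measurement was reported".

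Protocol 10.3.4 plans a negative binomial rate analysis for the hypoglycemia categories other than severe, and a logistic analysis of incidence in each category.

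SAP 6.12.4.1 lists among the derived event types "nocturnal hypoglycemia (documented and occurring between bedtime and waking". It ties the word 'documented' to a measurement: documented symptomatic, asymptomatic and "documented unspecified hypoglycemia) will be based on blood glucose (BG") at or below 70 mg/dL, with a further version below 54 mg/dL. In Table 6.6 the nocturnal rows, for both rate and incidence, carry footnote a, which begins "All documented hypoglycemia and the subcategories based on the thresholds of blood glucose". The rows are compared over eight periods: Weeks 0-4, 0-12, 0-26, 4-8, 8-12, 12-26, 26-52 and 0-52.

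**The concern.** The two documents use one label, 'nocturnal', for two different sets of events. The protocol's set takes in every qualifying event at night. The SAP's set takes in only those with a low glucose value on record. A severe event managed by another person at night, with no meter reading taken, belongs to the first set and not to the second.

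What is at stake is the content of a supportive safety result. A reader of the study report who takes the nocturnal rate to mean what Protocol 9.4.1 says would be looking at a narrower count, and no other planned table would show the missing night-time events as night-time events.

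**Working it through.** No figure in the plan depends on this definition, so there is nothing to reproduce. The check is a comparison of the texts.

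**Step 1: which night-time events count.**

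| Night-time event | Protocol 9.4.1 | SAP 6.12.4.1 and Table 6.6 |
|---|---|---|
| Documented, glucose ≤70 mg/dL | Yes | Yes |
| Severe, glucose ≤70 mg/dL recorded | Yes | Yes |
| Severe, no glucose reading | Yes | No |
| Probable symptomatic (no reading by definition) | Yes | No |

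**Step 2: is the SAP wording deliberate or loose?** Footnote a to Table 6.6 treats the nocturnal rows as documented subcategories split by glucose threshold. An event without a value cannot be placed in either threshold version. Text and table agree, so the restriction would be programmed as written.

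**Step 3: where the excluded events still count.**
- Severe events have their own rows ("Rate of severe hypoglycemic events (per patient per year / 100 years") and incidence rows, over five periods. They are also SAEs, and patients who have them are listed.
- Probable symptomatic events have their own rate and incidence rows over the same eight periods as the nocturnal rows.
- Both count as overall hypoglycemia. The protocol says of it: "This category combines all cases of hypoglycemia (documented hypoglycemia and probable symptomatic hypoglycemia, including" severe events. The SAP lists the overall category without redefining it, so I take the protocol definition to apply.
- None of these rows has a night/day split. The SAP's daytime row is also restricted to documented events, so a severe event without a reading falls in neither the night row nor the day row.

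**Step 4: what can be said about size.** Let *u* be the share of protocol-defined nocturnal events without a reading. For crude rates with the same exposure:

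SAP rate = (1 − *u*) × protocol rate.

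The absolute rate is low by the fraction *u*. For two arms with shares *u*₁ and *u*₀:

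SAP rate ratio = protocol rate ratio × (1 − *u*₁)/(1 − *u*₀).

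If *u*₁ = *u*₀ the ratio does not change. If they differ it moves, in a direction that depends on which is larger. For incidence, a patient whose only nocturnal events lack a reading changes from 'event' to 'no event'. The documents give no value for *u* in any arm, and no expected number of nocturnal, probable symptomatic or severe events, so neither quantity can be computed.

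**Step 5: is the narrowing justified anywhere?** SAP 6.1 says that changes to the protocol's analysis methods, with their justification, will be described in the SAP and/or the study report. The SAP gives none for this one.

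**The case against.** The strongest reply is that little is lost. Events without a reading leave one category and not the safety analysis, as Step 3 shows. The hypoglycemia objectives listed in the protocol and SAP concern severe, documented symptomatic and documented symptomatic postmeal events; nocturnal events appear in none of the primary, multiplicity adjusted or other secondary objectives. Documented-only night and day rows form a coherent pair that can be run at both thresholds. The SAP also allows further hypoglycemia analyses as needed, and the study report could still explain the choice. All of this stands, and it limits the weight of the point. It does not remove the conflict of definition or supply a night-time analysis of the excluded events.

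Four stronger readings are tempting, and the documents do not support them.
- A reader might infer that the SAP removes severe night-time events altogether. It does not: those with a recorded value of ≤70 mg/dL still qualify.
- A reader might infer that the comparison between arms is biased. The same rule applies in every arm, the baseline rate used as covariate is defined by the same category, and the main comparison is double-blind. Bias would need the share without a reading to differ by arm, and nothing in the documents shows that.
- A reader might take the SAP's revision history, which does not mention the change, as a sign that it was made silently. That history records main changes between SAP versions. Wording present since Version 1 would not appear there.
- A reader might infer that the daytime row also breaches the protocol. Protocol 9.4.1 defines no daytime category, so there is no conflict to correct.

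**Conclusion.** The discrepancy is real and can be read directly from the two texts. The nocturnal rate and incidence planned in the SAP do not measure the category defined in Protocol 9.4.1. They omit all night-time probable symptomatic events and those night-time severe events that have no reading. Wherever such events occur, the absolute rate is understated against the protocol definition. By how much cannot be stated from the documents, and an effect on the between-arm comparison is neither shown nor excluded. No confirmatory test and no listed secondary objective depends on it.

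The conclusion rests on two readings: that 'documented' in the SAP requires a glucose value, which its text and footnote a both support, and that the overall category keeps its protocol meaning. The point deserves correction because the nocturnal result is a named safety category and the change is small.

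**What to change.** In SAP 6.12.4.1 and Table 6.6, derive nocturnal hypoglycemia as in Protocol 9.4.1: documented at ≤70 mg/dL, probable symptomatic, or severe, between bedtime and waking. Derive the baseline rate covariate for that row on the same basis. Keep the present ≤70 and <54 mg/dL rows and relabel them 'documented nocturnal'.

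If a matching night/day pair is wanted, a daytime row on the same basis can be added. This is optional.

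The cost is one derivation flag and additional table rows. No new data are needed: Protocol 9.1.4.1 has hypoglycemic events entered in the eCOA diary with the glucose value if one was measured, and SAP 6.12.4.1 refers to a diary question on nocturnal occurrence.
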